2.3 Analysis sets

The Enrolled Set (ENR) includes all patients who signed an ICF and are assigned patient numbers.

The Safety Set (SAF) includes all patients who received at least one IVT injection of study treatment.

The Full Analysis Set (FAS) will be the same as the Safety Set in this study and will be used as primary population to analyze the efficacy endpoints.

Urgent Safety Measure Set (USM): If any subject needs Q4 treatment interval at any time point after initial loading phase then that subject qualify for USM.

The Per-Protocol Set (PPS) is a subset of patients in the FAS without PDs with impact. The list of PD criteria will be provided in edit checks specification (ECS) document.

Full Analysis Set Estimand (FAS-EST): The FAS-EST comprises all patients who are in FAS and did not discontinue treatment in the entire study due to COVID-19.

Per-Protocol Set Estimand (PPS-EST): The PPS-EST is a subset of patients of the FAS-EST without PDs with impact due to COVID-19.

When assessing the robustness of the overall efficacy conclusions, considerations will be given to the analysis based on the estimand using FAS-EST and PPS-EST. The expectation for comparing of both estimands is to have similar conclusions. Inconsistencies in the results will be examined and discussed in the CSR.

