2.6 Analysis of the primary objective

2.6.1 Primary endpoint

The primary objective of this study is to evaluate the effect of brolucizumab 6 mg on disease control. The primary efficacy endpoint is the proportion of patients with no disease activity at Week 16 in the study eye.

Estimation for the proportion of disease control involves only calculating the ratio of successes. In this study

Event: 1= no disease activity (disease control)

0= disease activity (failure)

Count: Frequency or number of patients with no disease activity (disease control) at Week 16.

Proportion: Number of patients with no disease activity (disease control) at Week 16/Total number of patients in the FAS.

The number of disease control patients at Week 16, total number of evaluable patients, percentage of disease control and 95% confidence interval (CI) using the Clopper-Pearson method will be provided.

Sensitivity analysis will be performed for primary endpoint using last observation carried forward (LOCF) method and considering disease activity for missing data at Week 16.

A sensitivity analysis in patients exposed and not-exposed to USM will be performed for below estimand.

- a) Proportion of patients with no disease activity at Week 16.
- b) Status of patients with disease activity before and after introduce of USM.

The above analysis will be done on the FAS and only on the study eye.

The analysis will be performed on the PPS, if there is more than a 10% difference in patients, between FAS and the PPS.

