5.5 Rule of exclusion criteria of analysis sets

Table 5-1 Protocol deviations that cause patients to be excluded

Deviation ID	Description of Deviation	Exclusion in Analyses	Severity code
INCL01	Signed informed consent not obtained	Excluded from FAS and PPS	1
INCL02	Age less than 50 year	Included in everything	0
INCL03	No CNV lesions or >18M	Excluded from FAS and PPS	1
INCL04a	>1 previous anti-VEGF	Excluded from FAS and PPS	1
INCL04b	<3 previous aVEGF injections	Excluded from FAS and PPS	1
INCL04c	Prev aVEGF intvl out of range	Included in everything	0
INCL05	No residual fluid	Excluded from FAS and PPS	1
INCL06	Study eye BCVA out of range	Excluded from PPS	2
EXCL01	Active inflammation/infection	Excluded from PPS	2
EXCL02	Fellow eye ocular disease	Included in everything	0
EXCL03	History of IOI	Included in everything	0
EXCL04	Poor quality images	Included in everything	0
EXCL05	Study eye atrophy or fibrosis	Included in everything	0
EXCL06	Study eye lesion area ≥50%	Included in everything	0
EXCL07	Study eye concomitant condition	Included in everything	0
EXCL08	Study eye macula damage	Included in everything	0
EXCL09	Study eye vitreous hemorrhage	Included in everything	0
EXCL10	Study eye uncontrolled glaucoma	Included in everything	0
EXCL11	Study eye aphakia	Included in everything	0
EXCL12	Other trt in study eye	Excluded from PPS	2
EXCL13	Steroids in study eye	Included in everything	0
EXCL14	Prior keratoplasty/vitrectomy	Included in everything	0
EXCL15a	Study eye surgery	Included in everything	0
EXCL15b	Study eye laser photocoagul	Included in everything	0
EXCL15c	Study eye macular surgery	Included in everything	0
EXCL16	Previous laser treatment	Included in everything	0

Deviation ID	Description of Deviation	Exclusion in Analyses	Severity code
EXCL17	previous brolucizumab trt study eye	Excluded from FAS and PPS	1
EXCL18	ESRD	Included in everything	0
EXCL19	Systemic drugs toxic to eye	Included in everything	0
EXCL20	Participation in another study	Excluded from PPS	2
EXCL21	Systemic anti-VEGF therapy	Included in everything	0
EXCL22	Stroke or myocardial infarction	Included in everything	0
EXCL23	Uncontrolled blood pressure	Included in everything	0
EXCL24	Medical condition impact	Included in everything	0
EXCL25	Malignancy	Included in everything	0
EXCL26	Hypersensitivity	Included in everything	0
EXCL27	Pregnant or nursing woman	Included in everything	0
EXCL28	WOCP	Included in everything	0
EXCL29	Minors/protected adults	Excluded from PPS	2

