COMD01	Prohibited medication/procedures	Included in everything	0
COMD02	Non-permitted steroid use	Included in everything	0
TRT01	Trt > 3 days after inj visit	Included in everything	0
TRT02	Missed injection visit	Included in everything	0
TRT03	Wrong IP/volume administered	Included in everything	2
TRT04	IVT interval<than 21 days	Included in everything	0
TRT05	TRT admin prior effic/safty eval	Included in everything	0
TRT06	COVID-19 Drug supply change	Included in everything	0
TRT07	COVID-19 Treatment not given	Included in everything	0
TRT08	Missed Injection loading phase	Excluded from FAS and PPS	1
TRT09	Missed Injection	Included in everything	0
TRT10	No Disease acty bt INJ is given	Included in everything	0
TRT11	Treatment given at EOS	Included in everything	0
TRT12	anti-VEGF therapy during tria	Included in everything	0
WITH01	Withdrew constn nt discontinued	Excluded from FAS and PPS	1
OTHER01	Missed mandatory visit	Excluded from PPS	2
OTHER02	Subject rescreened > once	Excluded from PPS analysis	0
OTHER03	New ICF is missing-rescreened	Excluded from FAS and PPS	1
OTHER04	Rescrn >14days w/o scr proc	Included in everything	0
OTHER05	Odysight used w/o consent	Included in everything	0
OTHER06	Temp excursion IP administered	Included in everything	0
OTHER07	SAE not reported	Included in everything	0
OTHER08	Crit met to failure	Included in everything	0
OTHER09	The patient done rescreening	Included in everything	0
OTHER10	COVID-19 Missed visit	Included in everything	0
OTHER11	COVID-19 Visit not at site	Included in everything	0
OTHER12	COVID-19 Assessment changed	Included in everything	0

Deviation ID	Description of Deviation	Exclusion in Analyses	Severity code
OTHER13	COVID-19 Discontinuation	Included in everything	0
OTHER14	Visit window > 7 days	Included in everything	0
OTHER15	Efficacy assessment not done	Excluded from PPS	2
OTHER16	Safety assessment not done	Included in everything	0
OTHER17	BCVA not done correctly	Included in everything	0
OTHER18	Trt regimen wrongly adjusted	Included in everything	0
OTHER19	Vital signs/safety call not done	Included in everything	0
OTHER20	Imaging analyzed after WoC	Included in everything	0

Table 5-2 Patient Classification

Analysis Set	Severity codes that cause a subject to be excluded
ENR	NA
FAS	1
PPS	1, 2
SAF	NA

6 Reference

[HAWK] ClinicalTrials.gov. Identifier NCT02307682. Available at <https://clinicaltrials.gov/ct2/show/NCT02307682> (link is external). Accessed November 2017.

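### The text defines the FAS as all treated patients, but the SAP's deviation tables remove nine deviation types from it, so the primary denominator is not determined

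*SAP*

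**What the plan says.** **Text definition.** Protocol 12.1 and SAP 2.3 use the same sentence: "The Full Analysis Set (FAS) will be the same as the Safety Set in this study". Both define the Safety Set as patients with at least one injection and attach no deviation criterion.

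**Table definition.** SAP 5.5, Table 5-1, assigns each deviation a severity code. Table 5-2 has a column headed "Severity codes that cause a subject to be excluded". It lists code 1 for the FAS, codes 1 and 2 for the PPS, and not applicable for the Safety Set. Nine rows carry code 1 and are marked as out of both FAS and PPS:

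- Eligibility: INCL03, INCL04a, INCL04b, INCL05 ("No residual fluid") and EXCL17.
- Consent: INCL01, WITH01 ("Withdrew constn nt discontinued") and OTHER03.
- Treatment: TRT08 ("Missed Injection loading phase").

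**Interim SAP.** Its section 2.3 gives a third wording: the Safety Set less patients who have a deviation with impact. Its Table 5-1 has the same nine code-1 rows.

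**Declared changes.** Section 4 of both SAPs answers that there are none.

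**Use of the set.** SAP 2.6.1 defines the primary proportion as "Number of patients with no disease activity (disease control) at Week 16/Total number of patients in the FAS". It also asks for the "total number of evaluable patients". After describing the LOCF and missing-as-active analyses it adds: "The above analysis will be done on the FAS and only on the study eye".

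**The concern.** A treated patient with a code-1 deviation is in the Safety Set under every rule, in the FAS under the text, and out of the FAS under the tables. A programmer working from SAP 2.3 and one working from Table 5-2 would build different primary populations, and nothing in the documents says which is right.

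Two features make this more than an editing slip. First, not all the exclusions are baseline eligibility failures. TRT08 happens after the first injection, and WITH01 may. A set of all treated patients exists to avoid removing people for what happens later. Second, no planned efficacy analysis puts the excluded patients back. LOCF and missing-as-active run on the FAS, and the PPS, FAS-EST and PPS-EST are all drawn from within it.

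The choice also bears on whether the PPS analysis is run. SAP 2.6.1 makes it conditional on a difference of more than 10% in patients between FAS and PPS. Protocol 12.4.4 lists the PPS repetition among its planned analyses without that condition.

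**Working it through.** **1. Are the two rules compatible?** They are compatible only if no treated patient has a code-1 deviation. SAP 2.4.3 and 2.5.1 summarize demographics and exposure on both the FAS and the Safety Set, which would be redundant if the sets were identical. SAP 2.4.2 tabulates reasons for exclusion from the sets but does not restore anyone.

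**2. Scale for comparison.** Protocol 12.8 plans p = 0.30 with precision d = 0.055. Then n = 1.96² × 0.30 × 0.70 / 0.055² = 266.7, against 265 stated (half-width at 265: 0.0552). With 10% dropout, 265 / 0.9 = 294.4, so 295 as stated. The sample size is not in question; 5.5 points is the yardstick.

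**3. Effect on the proportion.** With x controlled among N, removing k patients of whom c are controlled gives (x − c)/(N − k). Assumptions: 295 treated, all in the divisor, x = 89, so 89/295 = 30.2% (Clopper-Pearson 25.0 to 35.8). The values of k are assumed (about 2%, 5% and 10%); the documents give none.

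| k removed | none controlled | average rate | all controlled |
|---|---|---|---|
| 6 | 89/289 = 30.8% (25.5–36.5) | 87/289 = 30.1% | 83/289 = 28.7% (23.6–34.3) |
| 15 | 89/280 = 31.8% (26.4–37.6) | 84/280 = 30.0% | 74/280 = 26.4% (21.4–32.0) |
| 30 | 89/265 = 33.6% (27.9–39.6) | 80/265 = 30.2% | 59/265 = 22.3% (17.4–27.8) |

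Over the planning range of 25% to 35% (74/295 to 103/295), the largest shifts are 1.6 points down or 0.7 up for k = 6, and 4.0 down (74/295 to 59/280) or 1.9 up (103/295 to 103/280) for k = 15.

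**4. What a TRT08 removal does.** Protocol 12.4.3 censors efficacy data from the first treatment interruption. It does not say whether a missed loading injection is an interruption.

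- *If it is*, the Week 16 value is censored. If no earlier value is used, c = 0 for these patients. Removal then raises the proportion when the FAS total is the divisor, and leaves it unchanged when evaluable patients are.
- *If it is not*, the patient can have a Week 16 value, since protocol section 8 says missed visits should not automatically end participation. Removal can then move the result either way.

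Protocol 6.7.2.2 adds that a patient who misses Week 16 has the Week 8 or Week 14 values used for the primary endpoint. A removed patient without a Week 16 visit may therefore still have contributed.

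**5. PPS trigger.** Assume N = 295 and take the difference as a share of the FAS. Let c1 be the number of code-1 patients and c2 the number with code 2 only.

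- Text FAS: triggered when (c1 + c2)/295 > 0.10. With c1 = 6, c2 must be at least 24.
- Table FAS: triggered when c2/(295 − c1) > 0.10. With c1 = 6, c2/289 > 0.10, so c2 must be at least 29.

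With 6 code-1 patients and 24 to 28 code-2-only patients, the PPS analysis is run under the text and not under the tables.

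**The case against.** The primary analysis is a descriptive proportion with a confidence interval; there is no test or success threshold to flip. Exclusions will be listed by patient with reasons, so a reader of the report could see them. The counts of 6 and 15 have no basis in the documents, the shifts they give stay inside 5.5 points, and at the average rate the estimate barely moves. All of this stands and limits the seriousness, although the comparison with 5.5 points depends on the assumed count: with 30 removed, all of them controlled, the shift is 7.9 points. It does not settle which set is the FAS.

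Excluding clear eligibility failures from an efficacy set can also be defended. That stands as a design choice, but it has to be declared, and it does not cover TRT08.

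A reader might infer that the exclusions flatter the result, or that dropping patients with a missed loading injection biases it in a known direction. The documents do not support this: there are no counts, and step 4 shows that the direction depends on an unstated reading of the censoring rule. A reader might also infer that Table 5-1 cannot be applied because a missed Week 4 or Week 8 visit could fit TRT02 (code 0), OTHER01 (code 2) and TRT08 (code 1). It can be applied. Table 5-2 excludes on any listed code and code 0 restores nobody, so the strictest code governs.

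**Conclusion.** The contradiction is real and stands on the text alone. Protocol 12.1 and SAP 2.3 give one FAS, Tables 5-1 and 5-2 give another, the interim SAP gives a third wording, and Section 4 of both SAPs reports no change. The primary denominator is therefore not determined, and no planned analysis would reveal the consequence.

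Size and direction are unknown. The percentages above are bounds that assume 295 treated, 89 controlled and an invented number of exclusions; they are not estimates, and no bias has been demonstrated. This should be fixed because it concerns the primary population, and because SAP 2.15 reports that the interim analysis has been done in an open-label study. An unrecorded choice now would be made with outcomes visible.

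**What to change.** 1. Keep FAS = Safety Set, as in protocol 12.1, for the primary proportion and interval. Recode TRT08, INCL03, INCL04a, INCL04b, INCL05 and EXCL17 as PPS-only (code 2). TRT08 then matches OTHER01.
2. For INCL01, WITH01 and OTHER03, state one data-use rule consistent with protocol 9.1.2 and applicable law. If it removes treated patients from the FAS or the Safety Set, declare that in Section 4 as a departure from protocol 12.1 and SAP 2.3.
3. Use one FAS sentence in both SAPs.
4. Because the interim analysis has been performed, show the Table 5-1 version as a sensitivity analysis, with exclusion counts by code, if the two sets differ. If the sponsor prefers to keep the exclusions, declare them in Section 4 and also report the primary result on all treated patients.
5. Make text and code agree for TRT03 (final SAP: included everywhere, yet code 2) and OTHER02 (excluded from the PPS, yet code 0).

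Cost: edits to the SAP tables and dataset specifications, and a rerun of every FAS-based output (primary, secondary efficacy, disposition, deviations, demographics and exposure), not only the Week 16 primary table. No new data are needed.

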(1) To provide clarification and guidance on the early discontinuation of study treatment that is required for those subjects who are currently on q4w dosing beyond the first 3 monthly loading doses (“loading phase”) or would need q4w dosing beyond the “loading phase” based on the investigator’s assessment. This is as per the urgent safety measure dated 27-May-2021 based on CTH258AUS04 (MERLIN) Year 1 first interpretable results (FIR) indicating a higher frequency of IOI including Retinal Vasculitis (RV), and Retinal Vascular Occlusion (RO) in brolucizumab 6 mg q4w when compared to aflibercept 2 mg q4w (IOI: 9.3% vs 4.5% of which RV: 0.8% vs 0.0%; RO: 2.0% vs 0.0%, respectively).

(2) Additionally, as per the Urgent Safety Measure dated 10-August-2021, the results of the mechanistic study BASICHR0049 identified a causal link with an immune-mediated mechanism of the previously identified risk of Retinal vasculitis (RV), and/or Retinal vascular occlusion (RO), typically in the presence of IOI. The protocol is hence amended to require discontinuation of study treatment in subjects who develop these events.

(3) The safety sections were updated throughout the protocol including updating the Risks and Benefits section and creating a new section under Safety Monitoring to consolidate all the information regarding the risk mitigation into one section in the protocol. Additionally, as subjects treated with brolucizumab who experience intraocular inflammation may be at risk of developing retinal vasculitis and/or retinal vascular occlusion they should be closely monitored and the investigator needs to evaluate the appropriateness of continuing further with study treatment when IOI only (without RV and/or RO) is present.

(4) Finally, clarification is provided on record of prior Intraocular or periocular use of corticosteroids in the study eye and remove of the study timelines and number of sites

Changes to the protocol

Changes to specific sections of the protocol are shown in the track changes version of the protocol using strike through red font for deletions and red underlined for insertions.

Editorial changes and spelling corrections are done throughout the protocol.

Protocol sections changed in relation to urgent safety measures (USM) are:

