At Week 8, based on Investigator's judgment of visual and/or anatomic outcomes, the injection interval will be extended by 4 weeks at a time if there is no disease activity, as provided in the guidance to the Investigators, e.g. no change in visual acuity and in other signs of the disease (e.g. IRF, SRF, hemorrhage, leakage, etc.). From Week 16, the injection interval can be maintained on Q8 (or Q12 from Week 28) if the Investigator deems that the patient will not benefit from treatment interval extension, with a minimal interval of 8 weeks. If disease activity recurs, the injection interval should be shortened accordingly by 4 weeks at a time or to a minimal interval of 8 weeks. The injection interval can also be maintained if the Investigator deems that the patient will not benefit from injection interval extension (see [Section 6.7.2](#) for further details). Patients who require study treatment every 4 weeks after the initiation phase will be discontinued from further study treatment at the next visit.

At the Investigator's discretion, in case of interval extension, inspection visits can be performed at the midterm of the interval extension, e.g. 6 weeks after the last injection when the injection interval is extended from 4 weeks to 8 weeks. If there is no disease activity in the study eye at the inspection visit, as assessed by the Investigator, no treatment will be administered at this inspection visit; the next visit and injection will take place 2 weeks later, i.e. 8 weeks after the previous study treatment. If disease activity is observed by the Investigator in the study eye at the inspection visit at Week 14, the study treatment will be administered by the Investigator and the patient will be discontinued from further study treatment at the next visit. Inspection visits 10 weeks and 14 weeks after the last injection can be performed when the injection interval is extended from 8 weeks to 12 weeks and from 12 weeks to 16 weeks, respectively (see [Section 6.7.2](#)).

Follow-up Period: from Week 44/46 to Week 48/50

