12.4.4 Sensitivity and supportive analyses

In order to assess the robustness of the primary endpoint, sensitivity and supportive analyses are planned. These may include, but are not limited to:

- Imputation of missing data :
 - Considering missing data as disease activity
 - LOCF imputation
- Repetition of the primary analysis using the PPS.

Sensitivity estimand in exposed and non-exposed to the urgent safety measures: As a sensitivity analysis for the disease activity at Week 16, the proportion of subjects with no disease activity at Week 16 will be compared before and after the urgent safety measures were introduced. The analyses will be performed in FAS and PPS.

Further details about the analyses will be given in the SAP. Any major discrepancies in the results across analyses will be investigated as needed.

Age, baseline fluids type (IRF, SRF), number of previous antiVEGF injections, and time since nAMD diagnosis subgroup analyses will also be performed on the primary endpoint.

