1.1 Study design

This is a prospective, single-arm, open-label, multicenter study to evaluate the efficacy and safety of brolucizumab 6 mg in pretreated suboptimal anatomically controlled patients with nAMD.

Approximately 295 adult patients will be screened and included (10% dropout rate expected) in France.

Before inclusion in the study, a patient must have a washout period of 4 weeks to 8 weeks (from 26 to 62 days inclusive) *versus* his/her last administration of a licensed anti-VEGF drug (i.e. Lucentis®, Eylea®).

The maximum study duration for 1 patient is 48 to 50 weeks, according to the patient schedule.

[figure not shown]
The study will consist of 2 periods ([Figure 1-1](#)):

- Open-label Treatment Period (from Screening/Baseline (Day 1) to Week 44 or Week 46 according to patient schedule)
- Follow-up Period (from Week 44 to Week 48 or from Week 46 to Week 50 according to patient schedule)

According to the patient treatment schedule, the last treatment can be at Week 44 or Week 46. If the last treatment visit is at Week 46, the End-of-study visit will be at Week 50 (at least 4 weeks after the last injection) instead of at Week 48.

Patients will require attending 5 mandatory study visits: Screening/Baseline (Day 1), Weeks 4, 8, 16, and 48/50. The other visit time points will depend on the injection regimen of the patient.

Figure 1-1 Study design

a End of treatment: Week 38/40/42/44/46 according to treatment schedule.

b End of study: at least 4 weeks after the end of treatment. For patients receiving the last IVT at Week 46, the EOS Visit will be at Week 50, 4 weeks following their last treatment.

The fellow eye will be treated at the discretion of the Investigator.

The Screening Visit and the Baseline Visit are the same visit in this study. Patients will receive 3 initial doses every 4 weeks (Day 1, Week 4 and Week 8). From Week 8, based on Investigator's judgment of visual and/or anatomic outcomes, the injection interval can be maintained on Q4 regimen or extended by 4 weeks at a time if there is no disease activity, as per Investigators decision, e.g. no change in visual acuity and in other signs of the disease (e.g. IRF, SRF, hemorrhage, leakage, etc.). If disease activity recurs, the injection interval should be shortened accordingly by 4 weeks at a time or to a minimal interval of 4 weeks.

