Patients who show disease activity at any of visits after week 8 will be adjusted to treatment interval and will remain on this interval until the end of the study at Week 48/50.

At the Investigator's discretion, in case of interval extension, inspection visits can be performed at the midterm of the interval extension, e.g. 6 weeks after the last injection when the injection interval is extended from 4 weeks to 8 weeks. If there is no disease activity in the study eye at the inspection visit, as assessed by the Investigator, no treatment will be administered at this inspection visit; the next visit and injection will take place 2 weeks later, i.e. 8 weeks after the previous study treatment. If disease activity is observed by the Investigator in the study eye at the inspection visit, the study treatment will be administered by the Investigator; the injection interval will be reduced to 4 weeks and the next visit will be 4 weeks after the inspection visit. Similarly, inspection visits 10 weeks and 14 weeks after the last injection can be performed when the injection interval is extended from 8 weeks to 12 weeks and from 12 weeks to 16 weeks, respectively.

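### The SAP puts no date on exposure to the urgent safety measure, and its only membership rule (need for Q4) would split the Week 16 check on disease activity

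*SAP*

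**What the plan says.** **The planned check.** Protocol 12.4.4, under a label that speaks of patients exposed and non-exposed to the measures, says that "the proportion of subjects with no disease activity at Week 16 will be compared before and after the urgent safety measures were introduced". This is a calendar comparison, although the section gives no cut-off date. The date of the measure that restricted Q4 dosing appears in the rationale for Amendment 3: "This is as per the urgent safety measure dated 27-May-2021". The same rationale dates a second measure, on retinal vasculitis and occlusion, to 10 August 2021, and section 12.4.4 refers to measures in the plural.

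**The SAP version.** SAP 2.6.1 says "A sensitivity analysis in patients exposed and not-exposed to USM will be performed for below estimand" and lists two items. Item (a) is the Week 16 proportion. Item (b) is "Status of patients with disease activity before and after introduce of USM". Neither has a date. Both are to be done on the FAS. SAP 2.3 contains the only rule that assigns a patient to a USM group: "If any subject needs Q4 treatment interval at any time point after initial loading phase then that subject qualify for USM". SAP section 4 declares no change from the protocol. The interim SAP, which covers the Week 16 endpoint, has no USM set and no USM analysis.

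**The regimen.** Protocol section 3 now says "Patients who require study treatment every 4 weeks after the initiation phase will be discontinued from further study treatment at the next visit". SAP 1.1 still says that from Week 8 "the injection interval can be maintained on Q4 regimen or extended by 4 weeks at a time if there is no disease activity". For an eye active at an inspection visit 6 weeks after the last injection, SAP 1.1 says "the injection interval will be reduced to 4 weeks and the next visit will be 4 weeks after the inspection visit".

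**The concern.** The protocol's check asks whether the mid-trial change in allowed dosing altered the Week 16 result. For that, patients must be grouped by something fixed independently of their response, such as the date on which they reached the dosing decision. Need for Q4 is not of that kind. It is judged after baseline, it follows from the investigator's view of disease activity, and the rule in SAP 2.3 has no time limit, so events after Week 16 can decide membership. Grouping on it would compare patients largely according to the endpoint itself.

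A second issue comes from the same regimen change. Under the earlier regimen a patient could be injected between Week 8 and Week 16, so the Week 16 reading would come sooner after an injection. The primary proportion pools these readings with the others and has no rule for them. At stake is whether the report can say anything about the effect of the regimen change on its main figure.

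**Working it through.** **1. The plan's own figure.** Protocol 12.8 uses p = 0.30 and 265 observed patients for a half-width of 5.5 points. Check: 1.96 × √(0.30 × 0.70 / 265) = 0.0552. The figure reproduces. (SAP section 3 prints 5% beside a width of 11%; the width agrees with 5.5.)

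**2. What item (a) would show on the Q4-need set with no regimen effect.** Take p = 0.30 controlled at Week 16. Let q be the share of Week-16-active patients who enter the set, and r the share of Week-16-controlled patients who enter it. Neither is in the documents; both are assumptions.

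- Controlled within the set = 0.30r / (0.30r + 0.70q)
- Controlled outside it = 0.30(1−r) / (0.30(1−r) + 0.70(1−q))

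| q | r | In the set | Outside the set |
|---|---|---|---|
| 0.50 | 0.10 | 0.03/0.38 = 7.9% | 0.27/0.62 = 43.5% |
| 0.25 | 0.10 | 0.03/0.205 = 14.6% | 0.27/0.795 = 34.0% |
| 0.10 | 0.25 | 0.075/0.145 = 51.7% | 0.225/0.855 = 26.3% |

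The two proportions agree only when q = r, that is, when entry is unrelated to Week 16 status. Otherwise a difference appears, in either direction, although the regimen change did nothing.

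**3. What a calendar split would show.** With no regimen effect and no other time trend, the expected difference is zero. The 95% half-width of the difference at p = 0.30 and N = 265 is 1.96 × √(0.21/n₁ + 0.21/n₂). The split is not in the documents, so a range is shown:

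- 50/50: ±11.0 points
- 25/75: ±12.7 points
- 10/90: ±18.4 points

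**4. Injections between Week 8 and Week 16.** Time from last injection to the Week 16 reading is 16 − 8 = 8 weeks after a Week 8 dose, 16 − 12 = 4 weeks after a Week 12 dose, and 16 − 14 = 2 weeks after a Week 14 dose. The upward shift in the primary proportion is (share treated under the earlier regimen) × (share of those re-injected before Week 16) × (share of those controlled only because of it). All three are assumptions:

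- 0.10 × 0.20 × 0.10 = 0.2 points
- 0.25 × 0.40 × 0.30 = 3.0 points (about 8 of 265 patients)
- 0.50 × 0.40 × 0.50 = 10 points

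The planned half-width is 5.5 points, so the shift may be negligible or may exceed it.

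**The case against.** The strongest reply is that nothing was replaced. Exposed and non-exposed are the protocol's own labels for its before/after comparison, and SAP 2.6.1 repeats them. That section works on the FAS and never cites the USM set. Item (b) keeps the before/after wording, and the SAP's abbreviation list expands USM as the measure, not as a group of patients. SAP 2.9.1 plans adverse-event summaries by need of USM, which gives the Q4-need set another use. On this reading, section 4 is right to declare no change.

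Much of this stands. A reader might infer that the SAP has swapped the calendar comparison for an outcome-defined one. The documents do not say so. What remains is that item (a) is listed apart from item (b), only (b) carries the before/after wording, and anyone looking for the meaning of exposed finds a single membership rule, the one in 2.3. Item (b) does not fill the gap, because it has no date, no population rule and no statistic.

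A reader might also infer a very large contrast: if almost nobody in the set were controlled, and the set held 20%, 40% or 60% of patients, the rest would be controlled at 0.30/0.80 = 37.5%, 0.30/0.60 = 50% or 0.30/0.40 = 75%. That is a limiting case. Protocol 6.7.2.2 allows Q8 to be kept from Week 16, so activity need not mean Q4. Patients controlled at Week 16 can enter the set later. A patient controlled at Week 16 after a Week 12 injection would be in the set and controlled at once.

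Nor does each 5% of re-injected, inactive eyes add 5 points to the primary proportion. Some would have been controlled anyway.

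The Week 14 route is mostly closed under the current protocol. An eye active at Week 14 is injected and study treatment then stops (6.7.2.2), efficacy data are censored at that point (12.4.3), and the Week 16 visit is waived after the early-discontinuation visit (Table 8-1, footnote 16). That visit is nominally at Week 14 + 4 = Week 18, or Day 126, outside the SAP's Week 16 window of Day 106 to 118. If Week 16 is missed, the active Week 14 status is applied. Some room is left because protocol section 3 places discontinuation at the next visit, and SAP 2.1.1 says that data are 'used' where the protocol says 'censored'.

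Finally, this is a sensitivity analysis in a single-arm estimation study. Its definition cannot move the primary proportion.

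**Conclusion.** The point holds as a defect of definition. Exposure in SAP 2.6.1(a) has no date, and the only available rule is a post-baseline consequence of disease activity with no time limit. Run on that rule, the analysis would not measure the regimen change that protocol 12.4.4 sets out to check. The illustrations (7.9% versus 43.5%, 14.6% versus 34.0%, 51.7% versus 26.3%) rest on 30% controlled overall, no regimen effect, and assumed entry rates. They show that the contrast follows from those rates, not how large it would be in this trial.

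It is not established that the SAP mandates this split, that the contrast must be large, or that the primary proportion is materially inflated. The effect of injections between Week 8 and Week 16 is unknown, at 0.2 to 10 points under assumed inputs, and mainly concerns patients treated under the earlier regimen.

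**What to change.** 1. **Define exposure by calendar date** in SAP 2.3 and 2.6.1. Name the measure (27 May 2021, or the site's documented implementation date) and the anchor: the patient's Week 8 visit falling before, or on or after, that date. Week 8 is where the two regimens diverge. Report the Week 16 proportion with its 95% confidence interval in each group, and state that the comparison is imprecise. Give item (b) a population and a statistic, or merge it with (a).
2. **Rename the Q4-need set** and use it only for descriptive disposition and safety tables.
3. **Tabulate weeks since last injection at the Week 16 reading.** Add, as a sensitivity analysis only, a version of the endpoint in which patients injected after Week 8 and before that reading count as not controlled. This is an estimand choice and should not replace the primary analysis.
4. **Reconcile the texts.** SAP 1.1 and the protocol disagree on the regimen after loading, and SAP 2.1.1 and protocol 12.4.3 disagree on data after treatment stops. No view is taken here on which clinical rule is right. Record any resulting change in SAP section 4.

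The cost is SAP wording, a derived flag and one added table, all from visit and injection dates already collected. The sensitivity proportion in item 3 can only equal or fall below the main one.
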